| 4.0, 02May2023 | 
 Remove branded commercial product naming (ex: "Colgate hum") and update to more generic naming (throughout) Include subgroup of 50 participants where aMMP8 activity will be measured using rinse method Include "Peripheral Artery Disease (PAD)" in cardiovascular disease Update IMT and FMD measurements may occur before baseline and 8 weeks after the designated treatment visit |

1. INTRODUCTION

1.1. Statement of the Problem

The most common oral diseases initiate as silent or asymptomatic (i.e. caries and periodontal disease) with very few outward signs of a problem until the tissue destruction becomes noticeable and irreversible for some conditions. There is a need to identify biomarkers to alert the population of their potential risk of having or developing these silent oral diseases. There is also a recognized association between the risk of developing oral inflammatory diseases for those with systemic inflammatory conditions (and vice versa). It has been shown that cardiovascular disease (CVD), diabetes, and periodontal disease are prevalent conditions in individuals throughout the United States and around the world. Higher CVD risk has been associated with severe chronic periodontal disease. Diabetes and periodontitis are considered complex chronic diseases with an established bidirectional relationship. For example, controlling gingival inflammation and periodontal disease is more difficult in people with uncontrolled or poorly controlled diabetes. Similarly, there is evidence that those presenting with oral inflammatory diseases are at higher risk for developing diabetes and more difficulty with glucose control, and they are at increased risk for cardiovascular disease. Thus, it has become critically relevant to identify more targeted technologies and clinical strategies aiming to reduce the oral inflammatory burden. The clinical research described in this proposal has been designed to better understand the biological pathways involved in the reported connections of oral to overall health and to identify biomarkers associated with oral health and disease.

The Baseline Oral Health Health Study is a randomized controlled trial to evaluate the impact of regular, professional non-surgical Intensive Periodontal Therapy (scaling and root planing and optimal oral hygiene with associated professional oral health behavior advice), on oral health as well as whether such effects are associated with corresponding changes to biomarkers characterizing systemic health. The study will be conducted in partnership with Verily and the Project Baseline Team, Colgate, and the University of North Carolina. The study population (ie. eligible participants) may be recruited from Project Baseline Health Study and the Baseline Community Study (ie.registry). Recruitment of participants may be expanded outside of the Project Baseline Health Study and the Baseline Community Study (ie. registry) as needed to support the study enrollment target. The Project Baseline Health Study is a longitudinal cohort study which characterizes participants across clinical, molecular, imaging, sensor, self-reported, behavioral, psychological, environmental, or other health-related measurements from onsite and/or remote visits, continuous monitoring through sensor technology, and regular engagement via an online portal, and mobile app. The purpose of the Baseline Community Study (ie. registry) is to build a community of volunteers that are interested in engaging in their health and/or contributing to clinical research. The data collected in this study may be used to develop tools and technologies in future exploratory studies and analysis of health and disease.

The study population to be recruited may include participants diagnosed with cardiovascular disease and/or type 2 diabetes mellitus (including prediabetes) and eligible for periodontal intervention. The

study will use dental centers and an experienced dental team to manage the oral care provided in this study.

1.2. Outcomes

Primary

- Impact of non-surgical periodontal treatment on oral health as measured by changes in periodontal probing depths
- Correlations between changes in periodontal health and changes in systemic health measures:
 - Glycated hemoglobin (HbA1c) (prediabetic and type 2 diabetic cohorts)
 - Flow-mediated dilation

Secondary

- Impact of treatment on other oral health measures:
 - Bleeding on probing
 - Clinical attachment level
 - Dental plaque index
 - Gingival index
- Impact of treatment on systemic health measures:
 - Flow-mediated dilation
 - Glycated hemoglobin (HbA1c) (prediabetic and type 2 diabetic cohorts)
 - Carotid intima media thickness (IMT)
 - High sensitivity C-reactive protein (hs-CRP) (all cohorts)
 - Lipid profile: Total cholesterol/LDL cholesterol/Triglycerides
- Impact of treatment on emotional (affectional) state and beliefs about disease as measured by PANAS and PMT surveys

Exploratory

- Prevalence and severity of periodontal disease in screen-eligible participants at initial oral health screening
- Relationship between treatment on all other molecular analytes, including protein, metabolite and immune system inflammatory biomarkers and subgingival plaque microbiome
- Correlations among all other oral and systemic health metrics
- Correlations among oral and systemic health metrics with molecular analytes, including inflammatory biomarkers and subgingival plaque microbiome.

1.3. Summary of Research Plan

The Baseline Oral Health Study will enroll approximately 200 participants in the study with approximately 100 participants each within the Control Group and the Treatment Group. The study population will be recruited from the Project Baseline Health Study participants in the North Carolina region and may be expanded to include subjects recruited outside of the Project Baseline Health Study if the initial screening from the Project Baseline Health Study pool of participants in the North Carolina region does not fulfill study enrollment powering. Screening methods for eligible participants may include review of electronic health records (EHR) or other systems in compliance with local requirements. The participants enrolled in the study will then be randomized into a Control Group and Treatment Group. The screened participants that become eligible and consented to this study will be seen at dental health sites. UNC study team will be the Principal Investigating team for this protocol.

The periodontal disease study will be presented to eligible participants and those interested will be scheduled for a screening visit (S0). (See Figure 1). At the screening visit, participants will be consented and provided with an oral health assessment, initial X-Ray series (Full Mouth series and vertical bitewings) per standard of care, a point of care blood glucose test and will be scheduled to receive Screening Visit flow mediated dilation (FMD) and carotid intima media thickness (IMT) measurements. Those meeting in/ex criteria will be enrolled into the study and a Screening Visit 1 (S1) will be scheduled for those subjects who need hopeless teeth extracted. A Screening Visit 2 (S2) may be scheduled as a post-operative visit or to extract additional hopeless teeth depending on allotted time available for the Screening Visit visit 1 (S1). The subjects will additionally be scheduled for the Baseline visit (T0, see Figure 1). The Screening Visits should be scheduled to take place no later than 2 weeks before the scheduled Baseline visit.

At the Baseline visit, another oral health assessment will be conducted, along with collection of biospecimen samples ie. blood, stool (optional), saliva, plaque, tongue biofilm, and gingival crevicular fluid. Subjects will then be randomized using a 1:1 protocol to a standard care group (Control Group) and a therapy group (Treatment Group). The Control Group will receive an initial periodontal treatment consisting of a pre-procedural rinse and scaling & root planing (SRP). Subjects in the Control group should refrain from non-study periodontal treatments for the duration of the study. The Treatment Group will receive the same periodontal treatment in addition to having subgingival chlorhexidine irrigation. All subjects will also complete a set of questionnaires (PANAS & PMT) using an online form. A subset of 50 subjects from each group will be randomly selected to have oral images captured using an intra-oral scanner at Baseline and a subset of follow-up visits. Subjects in the Treatment Group will receive a commercial connected toothbrush, a stannous fluoride toothpaste , mouthwash , proxabrush , and floss to be used at home along with instructions on their use. Brush heads for the connected toothbrush will be replaced every 3 months and products (toothpaste, mouthwash, proxabrush, and floss) will be replenished at every site visit. Additionally, subjects in the

Treatment Group will also receive brief behavioral advice from dental professionals focusing mainly on motivation and acknowledgement. Subjects in the Control Group will receive no products during the course of the study. They will receive Colgate products which may include a commercial connected toothbrush, toothpaste, mouthwash, proxabrush, and floss at the end of the study.

For a subgroup of 50 individuals, levels of active matrix metalloproteinase-8 (aMMP-8) will also be measured quantitatively using rapid point of care (PoC) chairside aMMP-8 kits (Periosafe®, Dentognostics GmbH, Solingen, Germany). The additional samples will be collected from 4 sites on a tooth with probing depth $\geq 5\text{mm}$ on the same visit as GCF samples will be collected.

Subjects will be scheduled to receive flow mediated dilation (FMD) and carotid intima media thickness (IMT) measurements prior to Baseline and approximately 8 weeks after their Baseline visit. Also in those visits, for a subset of 50 individuals aMMP8 activity will be measured using rinse method following manufacturer instructions and the chair side data positive aMMP-8 test is based on a cutoff of 25 ng aMMP-8 per milliliter of filtrate derived from 5 mL mouthrinse

Subjects in both the Control and Treatment Group will attend 3 follow-up visits (respectively T1-T3, see Figure 1). At these visits, the Control Group will have a clinical exam and a biospecimen collection while the Treatment Group will have a biospecimen collection followed by a clinical exam, periodontal treatment consisting of scaling and root planing and chlorhexidine preprocedural rinse and chlorhexidine irrigation (Chlorhexidine Gluconate Oral Rinse, 0.12%), and will be provided with new products to support the oral hygiene regimen. Finally, during follow-up visits, subjects in the Treatment Group will also receive specific behavioral advice focusing on monitoring their progress (through use of brushing data), motivation and reinforcement. Depending on the progress of each subject, IF-THEN plans designed to overcome barriers in using the oral hygiene regimen can be deployed. Dental professionals will be providing scripted and standardized advice to subjects to the Treatment Group. All subjects (control and therapy group) will also complete a set of questionnaires (PANAS & PMT) using an online form. FMD and IMT will also be measured (approximately 8 weeks after T2).

A fourth follow-up visit, (T4, see Figure 1) occurs at approximately Month 12 and at this visit, all subjects (regardless of group assignment) will receive a clinical exam, biospecimen collection, and periodontal treatment including subgingival chlorhexidine irrigation. At this visit, the treatment group will receive brief behavioral advice focusing on motivation and support and both groups will complete a set of questionnaires (PANAS & PMT) using an online form.

Participants will be scheduled to receive FMD and IMT measurements approximately 8 weeks after their T4 visit.

The final follow-up visit (T5, see Figure 1), occurs at approximately 15 months after the Baseline visit. Both groups will receive a clinical exam and biospecimen collection. At T5, a second X-Ray series will be taken for qualitative analysis as part of the research purposes. The Control Group will be asked to fill out a questionnaire on the oral care products they used during the study. They will receive Colgate products which includes a commercial connected toothbrush, toothpaste, mouthwash, proxabrush, and dental floss at the end of the study.

After completion of the study, participants will be recommended to continue treatment with their usual dentist or other local dental professional. Finally, all subjects will complete a set of questionnaires (PANAS & PMT) using an online form.

Subjects who have been randomly selected to receive intraoral scans at Baseline will also receive intraoral scans at T2, T4, and T5.

In between visits starting at the end of the face-to-face visit at T0 and ending after T4, Treatment Group subjects will also receive additional support via text messages. This support will aim on motivation and reinforcement in order to support the use of the oral hygiene regimen at home during the study and to assist with the creation of long-term habits around good oral hygiene practices.

[figure not shown]

Figure 1: Clinical Design. Eligible subjects are screened at an initial screening visit (S0) and those meeting the in/ex criteria are enrolled and scheduled for 7 subsequent visits. Screening Visit visits (S1,S2) may be scheduled to extract hopeless teeth or to perform post-operative treatments as assessed during the screening visit S0 and as required to be eligible to be enrolled in the study. A Screening Visit visit will also be completed to take FMD and IMT measurements. At the Baseline visit (T0), a baseline oral health assessment will be conducted along with an initial periodontal treatment and randomization to Control or Treatment Groups. Subjects randomized to the Treatment Group will receive distributions of home regimen products. Four follow-up visits (T1-T4) will then take place approximately every three months. All subjects, irrespective of group assignment, will receive a second (and final) periodontal treatment at T4. The final visit (T5) will take place approximately 3 months after the cessation of treatment for both groups. Biospecimen will be collected for all 6 visits (T0-T5). Intra-oral scans for the selected subset of subjects will be captured at T0, T2, T4, and T5. Study will include two X-Rays (Full Mouth Series), to be taken at S0 (per standard of care) and at T5 for qualitative research purposes. *X-Rays (S0 Full Mouth Series) should be completed at the end of the screening phase during S0.

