2.3.3. Clinical Measures

Carotid IMT Measurement:

Carotid intima-media thickness (IMT): Subclinical atherosclerosis will be assessed by measuring carotid IMT. Longitudinal ultrasound images of the distal 1 cm segments of the right and left common carotid arteries, carotid bulbs, and internal carotid arteries will be acquired. IMT will be measured as the distance between luminal-intimal interface and medial-adventitial interface. Mean IMT will be calculated as the average of all measurements; mean maximum IMT will be calculated as the average of maximum wall thicknesses for each of the regions.

Flow mediated dilation (FMD): Vascular endothelial function will be assessed by measuring flow-mediated dilation (FMD) of the brachial artery at Screening Visit, after baseline, 6 month follow-up, and 1-year follow-up. Ultrasound images of the right brachial artery and Doppler measures of arterial flow will be acquired before and after reactive hyperemia is induced by inflating a pneumatic occlusion cuff placed around the lower arm. FMD will be calculated as the percent change in arterial diameter from baseline. Peak hyperemic flow will be expressed as the time-velocity integral of the Doppler velocity .

*IMT and FMD measurements may occur before baseline and 8 weeks after the designated treatment visit.

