3. PARTICIPANT FOLLOW-UP

3.1. Overview

All subjects enrolled in the Baseline Oral Health Health Study will report to the clinical facility having refrained from any oral hygiene procedures for twelve hours prior to their examination and having refrained from eating, drinking or using tobacco products, including chewing tobacco, for twelve hours prior to their examination. Subjects will be followed-up for cardiovascular, HbA1c and periodontal conditions. Follow-up contacts begin approximately 3 months after Baseline (T0) visit and will reoccur at approximately 6, 9, 12, and 15 months after Baseline (T0) visit. A contact window of plus or minus 28 days around each Follow-up visit's (T1-T5) target date is allowed. Follow-ups will include review of current medications, adverse events, cardiovascular endpoint inquiry and assessment, clinical data collection (blood pressure, heart rate, weight, and height), dental history since last contact, oral periodontal examination and indices, and sample collections (i.e. blood, saliva, dental plaque, tongue biofilm, GCF, and stool when applicable). All subjects will have an IMT and FMD analysis prior to Baseline and approximately 8 weeks after the Baseline (T0), Follow-up 2 (T2), and Follow-up 4 (T4) visits.

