3.2. Visit Schedule

| Visit | Screening (S0) | Screening Visit 1-2 ¹ (S1-S2) | Baseline (T0) | Follow-up 1 (T1) | Follow-up 2 (T2) | Follow-up 3 (T3) | Follow-up 4 (T4) | Follow-up 5 (Final visit) (T5) |
|---------------------------|----------------|--|---------------|-------------------|--------------------|--------------------|--------------------|--------------------------------|
| Timeline | -90 days | -89 to -14 days | 0 day | 90 days ± 28 days | 180 days ± 28 days | 270 days ± 28 days | 360 days ± 28 days | 450 day ± 28 days |
| Type of visit | Dental Clinic | Dental Clinic | Dental Clinic | Dental Clinic | Dental Clinic | Dental Clinic | Dental Clinic | Dental Clinic |
| Informed Consent | x | | | | | | | |
| Dental Screen | x | | | | | | | |
| Extractions ² | | x ² | | | | | | |
| Vitals | x | x | x | x | x | x | x | x |
| Medical History | x | x | x | x | x | x | x | x |
| Diet Questionnaire | | | x | x | x | x | x | x |
| PANAS | | | X (online) | X (online) | X (online) | X (online) | X (online) | X (online) |
| PMT | | | X (online) | X (online) | X (online) | X (online) | X (online) | X (online) |
| X-Ray Full Mouth Series | x | | | | | | | x |
| PreProcedural Rinse | | | x | x* | x* | x* | x | |
| Periodontal Exam | x | | x | x | x | x | x | x |
| Dental CRFs | x | x | x | x | x | x | x | x |
| Biological Samples: Blood | x*** | | x | x | x | x | x | x |

| | | | | | | | | |
|---|---|--|-----|----|-----|----|-----|-----|
| Biological Samples: GCF, [POC aMMP8 (subset)], saliva, plaque, tongue biofilm | | | x | x | x | x | x | x |
| Stool samples (optional) | | | x | | x | | x | |
| POC aMMP8 mouthrinse | | | x | | x | | x | |
| Carotid IMT Ultrasound | x | | x | | x | | x | |
| Flow- Mediated Dilation | x | | x | | x | | x | |
| Periodontal treatment | | | x | x* | x* | x* | x | |
| Intra-oral Scan (select subset) | | | x** | | x** | | x** | x** |
| Behavioral support (on site) | | | x* | x* | x* | x* | x* | |
| Review Brushing Data from Connected Brush | | | x* | x* | x* | x* | x* | x* |
| Distribute at-home regimen | | | x* | x* | x* | x* | x* | x |

¹Screening Visit (1-2) can span two days depending on the allotted time for extractions

²Extractions will occur as needed based on dental assessment

*Treatment group only

**For approximately 50 subjects from each of Control and Treatment groups

*** Blood sample - finger prick

Additional assessments would be conducted in addition to the above listed Schedule of Assessments. This may include:

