 - a. Debride again with the Cavitron under continuous water irrigation, approximately 30 seconds per tooth, from the buccal and the lingual as in the initial debridement. Concentrate on those areas that feel rough upon root surface testing. The total

ultrasonic debridement (initial and final) per 2 quadrants may use 500-1,000 ml of water.

- b. If the interdental papillae become detached as a result of the hand curette instrumentation, sutures may be used on buccal and lingual papillae over the interproximal bone with single interproximal suture. Use 4.0 silk suture material, no dressing is to be used.

7. Chlorhexidine Irrigation

- a. Subjects randomized to Treatment Group will receive application of Chlorhexidine as a preprocedural rinse and as part of the subgingival scaling and root planing treatment. Upon completion of SRP all sites will be irrigated with CHX rinse using a syringe.
- b. Patients randomized to the Control Treatment Group will receive application of Chlorhexidine, as preprocedural rinse and locally at Visit 4 (15 months), following completion of periodontal treatment. Upon completion of SRP all sites will be irrigated with CHX rinse using a syringe.

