14.1.2. Primary Analyses

Analyses associated with the first primary outcome, the impact of treatment on oral health measures, will be performed using generalized estimating equations (GEE) methods. Longitudinal outcomes in the Treated vs. Control groups will be compared and will include all subjects who were randomized and their data from visits T1 - T4 based on intent-to-treat (ITT) group assignment.

The second primary outcome, association between changes in oral health and changes in systemic health, will be evaluated using correlation analysis. Changes in the measures of oral and systemic health between Baseline (T0) and follow-up visit 4 (T4) will be calculated for all subjects in the study who complete the T4 visit. The strength of correlations between changes in oral health and change in HbA_{1c} (in subjects with prediabetes or type 2 diabetes) or change in flow mediated dilation will be evaluated.

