14.1.3. Secondary Analyses

All secondary outcomes will be evaluated using the ITT population and GEE methodology. Systemic outcomes that are only applicable to a particular comorbid disease subgroup will only be evaluated in that population. Specifically, flow-mediated dilation and Carotid intima media thickness (IMT) will be evaluated in all subjects.

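### The year-1 FMD and IMT scan comes about 8 weeks after the Control Group is re-treated at T4, so it does not isolate the 12-month contrast

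*Combined protocol and SAP*

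**What the plan says.** - **Treatment at T4.** Section 1.3 states that at this visit, about month 12, "all subjects (regardless of group assignment) will receive a clinical exam, biospecimen collection, and periodontal treatment including subgingival chlorhexidine irrigation". Sections 3.4 and 4.3.1 agree that Control has SRP at Baseline and again at Visit 4, 12 months after Baseline.
- **Scan timing.** Section 1.3: "Participants will be scheduled to receive FMD and IMT measurements approximately 8 weeks after their T4 visit". Section 3.1 gives the whole series, with the last scan tied to T4 (the excerpt stops just before that visit's number): "All subjects will have an IMT and FMD analysis prior to Baseline and approximately 8 weeks after the Baseline (T0), Follow-up 2 (T2), and Follow-up". Section 2.3.3 is more permissive ("IMT and FMD measurements may occur before baseline and 8 weeks after the designated treatment visit") and describes the last FMD as the 1-year measurement.
- **Visit table (3.2).** The scans are marked at screening, T0, T2 and T4 with no offset: "Flow- Mediated Dilation | x | | x | | x | | x". Section 3.3 lists IMT only at baseline and one year.
- **Analysis.** The primary GEE (14.1.2) "will include all subjects who were randomized and their data from visits T1 - T4 based on intent-to-treat (ITT) group assignment". The second primary outcome correlates T0-to-T4 change in oral health with T0-to-T4 change in HbA1c or FMD. For secondary outcomes, which include the treatment effect on FMD and IMT, 14.1.3 says "All secondary outcomes will be evaluated using the ITT population and GEE methodology" and names no visits.
- **A conflicting date.** Section 4.3.1.1 gives Control's chlorhexidine "as preprocedural rinse and locally at Visit 4 (15 months), following completion of periodontal treatment", whereas 3.4 and 4.3.1 put Visit 4 at 12 months.

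**The concern.** Up to T4 the trial compares repeated therapy with a single SRP. At T4 the Control Group is treated as well. Probing, blood and oral samples at T4 are listed before that treatment, but FMD and IMT are taken about 8 weeks after it. The scan called the 1-year value therefore reflects a Control Group that has just been re-treated.

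Three things follow.

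1. The between-arm vascular comparison at year 1 is likely pulled toward no difference. A null result could be mistaken for absence of a 12-month systemic effect.
2. The FMD correlation is mismatched at its follow-up end. A Control mouth that has relapsed is scored as relapsed at T4, is then treated, and only then has its FMD measured.
3. Because 14.1.3 sets no visit limit, the post-T4 scan and the T5 data enter the secondary between-arm comparisons, whereas the primary GEE stops at T4.

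**Working it through.** **1. The plan's own between-arm figure.** Section 14.2 powers only probing depth: reductions of 0.88 (SD 0.5) and 0.63 (SD 0.59) mm, two-sided 0.05, 90% power. The averaged variance is (0.25 + 0.3481)/2 = 0.299, so SD = 0.547. Then n = 2 × (1.960 + 1.282)² × 0.299 / 0.25² = 100.6, or 101 per group against 100 stated. The figure reproduces. No corresponding figure is given for FMD or IMT.

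**2. Timeline.** Visit days and the ±28-day window come from 3.2; the offset is 56 days. Sessions are scheduled full-mouth sessions (Treatment at T0 to T4, Control at T0 and T4), leaving aside the site-directed care in 2.2.

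| Scan | Nominal day (window) | Sessions, Treatment vs Control | Days since last session, Treatment vs Control |
|---|---|---|---|
| after T0 | 0 + 56 = 56 | 1 vs 1 | 56 vs 56 |
| after T2 | 180 + 56 = 236 (208–264) | 3 vs 1 | 56 vs 236 |
| after T4 | 360 + 56 = 416 (388–444) | 5 vs 2 | 56 vs 56 |

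Only the post-T2 scan, at about month 8, compares repeated therapy with a single SRP. If IMT is done only at baseline and one year, as 3.3 says, its sole follow-up scan comes after Control's re-treatment.

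**3. Between-arm loss (assumption only).** Suppose the undiluted standardised effect equals the probing-depth value, 0.25/0.547 = 0.457, with 100 per arm, and a fraction f survives at the post-T4 scan. Power is about Φ(0.457 f √50 − 1.96):

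| f | 1 | 0.75 | 0.50 | 0.25 |
|---|---|---|---|---|
| Power | 90% | 68% | 37% | 13% |

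Nothing in the documents fixes f or the FMD/IMT effect.

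**4. Correlation (assumption only).** Suppose the arms are equal in size, variances and mean changes, the true r is 0.30, and Control keeps a fraction g of the association. The pooled r is about 0.30(1 + g)/2. With 200 completers, Fisher's z gives power Φ(atanh(r) × √197 − 1.96):

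| g | 1 | 0.5 | 0 |
|---|---|---|---|
| Pooled r | 0.30 | 0.225 | 0.15 |
| Power | 99% | 89% | 56% |

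The last column is the worst case. Any between-arm difference in mean change would alter these values.

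**5. Analysis windows side by side.** The primary GEE uses T1 to T4. The secondary GEE names no visits. Vascular data exist after the T4 treatment (post-T4 scan), and so do T5 clinical, blood and questionnaire data, so both enter as written. No FMD or IMT is scheduled at T5.

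**The case against.** **The arms stay different.** A reader might call T4 a crossover and infer that the last scan cannot show a treatment effect. The documents do not support that. Control already had SRP at Baseline, reaches the last scan with 2 sessions against 5, receives no study products until the end of the study, and gets neither the behavioural advice nor the text messages. A positive result would still be informative. This stands.

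**The offset looks deliberate.** Scans are tied to 8 weeks after a treatment visit, and at the post-T4 scan both arms are equally far from their last SRP. That scan can be defended as a comparison of cumulative regimens. But it is a different quantity from the 12-month contrast, and the plan does not say which is meant.

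**The visit table could be taken literally.** A scan at T4 before treatment would remove the problem. However, 1.3 and 3.1 both state the 8-week delay. The table also marks T0 in addition to screening, which fits a delayed scan better than two scans before treatment.

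**The loss is easily overstated.** Suppose the GEE averages the three scans equally and a fraction k of the post-T2 contrast is seen at the other two. The average is then (1 + 2k)/3, and a reader might infer that T4 costs 9, 4 or 2.25 times the subjects for k = 0, 0.25 or 0.5. That charges T4 with the loss at the post-T0 scan, where each arm has had one session. With an undiluted year-1 scan the average would be (2 + k)/3, so the T4 share is ((2 + k)/(1 + 2k))² = 4, 2.25 or 1.56. Even this uses one k for two very different contrasts and assumes averaging, which the plan does not specify.

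**A separate Statistical Analysis Plan may deal with it.** Sections 2.6 and 14.1.4 refer to one, and its text is not part of the document reviewed. It could settle the analysis window, but wording cannot supply a scan that was not taken before treatment.

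**Conclusion.** The point holds: following 1.3 and 3.1, the year-1 FMD/IMT scan does not isolate the 12-month contrast of repeated therapy with a single SRP. The contrast is probably diluted toward no difference but still present. A null result could not be read as no 12-month vascular effect; to say that the scan shows nothing would go too far.

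The T0-to-T4 FMD correlation pairs an exam listed before the T4 treatment with a scan about 8 weeks after it. The secondary GEE admits data from after Control's re-treatment.

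The size of the loss cannot be derived from the documents; every power or correlation value above is an illustration. The timeline assumes the nominal visit days and that T4 procedures occur in the order listed in 1.3.

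This is a should-fix. The between-arm vascular outcomes are secondary, the affected primary element is a correlation whose HbA1c part is untouched, and the probing-depth comparison is not affected.

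**What to change.** **If scans can still be moved.** Take the year-1 FMD/IMT scan before the T4 periodontal treatment, within the T4 window. The number of scans is unchanged. The cost is a scheduling amendment, and a scan about 3 months (360 − 270 = 90 days) instead of 8 weeks after the Treatment Group's previous session.

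**If scans are already done.**

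- (a) Limit the secondary between-arm GEEs to data collected before the T4 treatment. The post-T2 scan then becomes the last vascular comparison. Report the post-T4 scan and T5 separately, labelled as after Control's re-treatment. The cost is that the randomised vascular comparison ends at about month 8.
- (b) For the FMD correlation, do not pair the post-T4 scan with the T4 exam. Either of two pairings would serve:
  - Pair the post-T4 scan with probing-depth change to T5, since the visit table schedules no treatment between them. Section 3.4 can be read as extending Treatment Group care to follow-up 5, so confirm this first.
  - Pair the post-T2 scan with the T3 exam, only in subjects whose T3 exam came after the scan. The nominal gap is 270 − 236 = 34 days, but the windows allow 242 − 264 = −22 to 298 − 208 = +90 days, so T3 treatment can precede the scan. The cost is some lost subjects.

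**In either case.** State which scan is the 12-month value and how later data enter each analysis. Reconcile the scan timing in 1.3, 2.3.3 and 3.1 with the visit table in 3.2 and with the IMT schedule in 3.3. Reconcile the 15 months for Visit 4 in 4.3.1.1 with the 12 months in 3.4 and 4.3.1.
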